### **21. Study Registration and Results**

#### ***21.1. Study Registration***

To comply with applicable laws and regulations, the study will be registered on a publicly accessible database.

#### ***21.2. Clinical Investigation Report***

Study results will be made available in accordance with the legal requirements and the recognized ethical principles, in accordance with the BSC Policy. A Clinical Investigation Report will be made available to all investigators, IRB/EC/REB and regulatory authorities, as applicable in accordance with the BSC Policy and local requirements. As applicable an abbreviated Clinical Investigation Report will be made available on a publicly accessible database.

#### ***21.3. Publication Policy***

BSC requires disclosure of its involvement as a sponsor or financial supporter in any publication or presentation relating to a BSC study or its results. BSC may submit study results for publication (regardless of study outcome) following the conclusion or termination of the study. BSC adheres to the Contributorship Criteria set forth in the Uniform Requirements of the International Committee of Medical Journal Editors (ICMJE; <http://www.icmje.org>). In order to ensure the public disclosure of study results in a timely manner, while maintaining an unbiased presentation of study outcomes, BSC personnel may assist authors and investigators in publication preparation provided the following guidelines are followed:

- All authorship and contributorship requirements as described above must be followed.
- BSC involvement in the publication preparation and the BSC Publication Policy should be discussed with the Coordinating Principal Investigator(s) and/or Executive/Steering Committee at the onset of the project.
- The First and Senior authors are the primary drivers of decisions regarding publication content, review, approval, and submission.

The data, analytic methods, and study materials for this clinical trial may be made available to other researchers in accordance with the BSC Data Sharing Policy (<https://www.bostonscientific.com/>).

## 23. Abbreviations and Definitions

### 23.1. Abbreviations

Abbreviations are shown in **Table 23.1-1**

**Table 23.1-1: Abbreviations**

Abbreviation/Acronym	Term
ADE	Adverse Device Effect
AE	Adverse Event
AT	As Treated
BPH	Benign Prostatic Hyperplasia
BPO	Benign Prostatic Obstruction
BSC	Boston Scientific Corporation
CA	Competent Authority
CBC	Complete Blood Count
CEC	Clinical Events Committee
CFR	Code of Federal Regulations
CI	Confidence Interval
CRF	Case Report Form
CRO	Contract Research Organization
CT	Computed Tomography
EAU	European Association of Urology
EC	Ethics Committee
eCRF	Electronic Case Report Form
EDC	Electronic Data Capture
ESWL	Extracorporeal Shock Wave Lithotripsy
EU	European Union
FDA	Food and Drug Administration
GCP	Good Clinical Practice
GDPR	Global Data Protection
H & P	History and Physical
HIPAA	Health Information Portability and Accountability Act
HoLEP	Holmium Laser Enucleation of the Prostate
Ho: YAG	Holmium: yttrium-aluminum-garnet Laser
ICF	Informed Consent Form
ICH	International Conference on Harmonization
ICMJE	International Committee of Medical Journal Editors
IFU	Instructions For Use
INR	International Normalized Ratio
IPSS	International Prostate Symptom Score
IRB	Institutional Review Board
ISO	International Organization for Standardization
ITT	Intent To Treat
LUTS	Lower Urinary Tract Symptoms

**Table 23.1-1: Abbreviations**

Abbreviation/Acronym	Term
MET	Medical Expulsive Therapy
NIH	National Institutes of Health
OHRP	Office for Human Research Protections
PCNL	Percutaneous Nephrolithotomy Procedures
PP	Per Protocol
PSA	Prostate-Specific Antigen
PT	Prothrombin Time
PTT	Partial Thromboplastin Time
PUL	Prostatic Urethral Lift
PVR	Post Void Residual
QOL	Quality of Life
REB	Research Ethics Board
SAE	Serious Adverse Event
SADE	Serious Adverse Device Effect
SFR	Stone Free Rate
SOC	Standard of Care
TUIP	Transurethral Incision of Prostate
TURP	Transurethral Resection of Prostate
UADE	Unanticipated Adverse Device Effects
UPN	Universal Product Number
USADE	Unanticipated Serious Adverse Device Effects
UTI	Urinary Tract Infection

**23.2. Definitions**

Terms are defined in **Table 23.2-1**.

**Table 23.2-1: Definitions**

Term	Definition
Adverse Device Effect (ADE)	See Table 17.2-1: Safety Definitions
Adverse Event (ADE)	See Table 17.2-1: Safety Definitions
As Treated	All subjects for whom treatment is attempted.
Clinical Events Committee	An independent or group of physicians with trial relevant therapeutic expertise whose purpose is to review and adjudicate important endpoints and/or specific adverse events.
Data Subject	In GDPR: Any living individual to whom the personal data relates. Examples of data subjects in this study are physicians and subjects.

Term	Definition
Deviation (Clinical Protocol)	A departure from the requirements established in the clinical trial protocol (e.g., inclusion/exclusion criteria; visit windows, required procedures, and any specified consenting process requirements).
Device Deficiency	See Table 17.2-1: Safety Definitions
General Data Protection Regulation (GDPR)	The General Data Protection Regulation (GDPR) is a European law that will govern how companies (whether EU-based or not) use personal data.
Hospitalization	See Table 17.2-1: Safety Definitions
Intent-To-Treat	A subject who signs the informed consent, meets eligibility criteria, and for whom the Lithotripsy/HoLEP procedure is initiated but not completed (first incision). The original ICF and screening documentation for intent to treat patients should be maintained in the site's files. These patients are followed in accordance with the study follow up schedule for safety and count toward enrollment.
Monitoring	EN ISO 14155:2020-3.29 - Act of overseeing the progress of a clinical investigation to ensure that it is conducted, recorded, and reported in accordance with the CIP, written procedures, this document, and the applicable regulatory requirements.  ICH E6 1.38 - The act of overseeing the progress of a clinical study and of ensuring that it is conducted, recorded, and reported in accordance with the protocol, Standard Operating Procedures (SOPs), GCP, and the applicable regulatory requirement(s).  FDA Guidance - Generally refers to the methods used by sponsors of investigational studies, or CROs delegated responsibilities for the conduct of such studies, to oversee the conduct of and reporting of data from clinical investigations, including appropriate investigator supervision of study site staff and third-party contractors.
Multi-center study	A clinical trial conducted according to a single protocol but at more than one site, and therefore carried out by more than one investigator.
Per Protocol	All subjects in the As Treated Population who have no major protocol deviations.
Personal Data	GDPR defines "Personal data" to be any information relating to an identified or identifiable natural person ('data subject'); an identifiable natural person is one who can be identified, directly or indirectly, in particular by reference to an identifier such as a name, an identification number, location data, an online identifier or to one or more factors specific to the physical, physiological, genetic, mental, economic, cultural or social identity of that natural person.
Point of Enrollment	Time at which, following recruitment, a subject signs and dates the informed consent form
Processing	Any use of personal data by BSC (or a third party on behalf of BSC), including data collection, data sharing, anonymization, and data storage (note the mere storage of data is considered as processing).

Term	Definition
RAVE	Proprietary electronic data capture system for capturing, managing and reporting clinical study data.
Recruitment	Active efforts to identify subjects who may be suitable for enrollment in the clinical investigation.
Sensitive Personal Data	GDPR defines “Sensitive personal” data as a subset of Personal Data, which, due to their nature have been classified as deserving additional privacy and security protections because their processing may create a risk for an individual’s fundamental right and freedom.
Serious Adverse Device Effect (SADE)	See Table 17.2-1: Safety Definitions
Serious Adverse Event (SAE)	See Table 17.2-1: Safety Definitions
Site Noncompliance	A departure from the regulations established by the relevant regulatory authorities. Includes all clinical site noncompliance that does not represent a direct deviation from the clinical trial protocol, e.g. IRB/IEC and sponsor reporting, device storage and accountability, staff qualifications and training, facilities, and equipment required to conduct the clinical trial, collection and documentation of data in source documents and CRFs, investigator oversight, etc.
Source Document	Original or certified copy of printed, optical or electronic document containing source data ( Ref. ISO 14155-2020 )

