### **10.10. *Study Completion***

Each subject in the Lithotripsy cohort will be followed up to 60 days post discharge from final Flexiva Pulse holmium laser Lithotripsy procedure per site's SOC. Each subject in the BPH cohort will be followed up to 6 months (180 days + 60 days) post discharge from HoLEP procedure per site's SOC. All subjects completing the last follow-up visit per site's SOC and their respective cohorts, will be considered to have completed the study. Subjects with any ongoing Adverse Events at the end of the study should be followed per institutions' standard of care.

If subject in the Lithotripsy cohort is undergoing a multi-staged lithotripsy procedure that does not use the Flexiva Pulse Laser Fibers, then subject should be exited from the study at the time of the additional procedure.

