#### **11.1.2.2. Statistical Methods**

Lithotripsy procedure cohort: The proportion of subjects who achieved stone clearance at 1 month follow-up post lithotripsy procedure will be calculated.

BPH procedure cohort: The change of IPSS total score at 3-month and 6-month post BPH procedure from baseline will be summarized using descriptive statistics. The same analysis will be performed for subjects with and without catheter at baseline if applicable.

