### ***11.2. General Statistical Methods***

#### **11.2.1. Analysis Sets**

The Intent-to-Treat (ITT) subject population includes all subjects who provide written informed consent to be enrolled into the study, and have the Lithotripsy or BPH procedure attempted.

The As Treated (AT) subject population includes all the ITT subjects who had the Lithotripsy or BPH procedure completed.

The Per Protocol (PP) subject population includes all the AT subjects who also meet all eligibility criteria and have no major protocol deviations.

The primary analysis of all the endpoints will be performed for the ITT population. Efficacy endpoints will be evaluated for the PP population as a sensitivity analysis and safety endpoints will be evaluated for the AS population as a sensitivity analysis.

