## **11.3. *Data Analyses***

The analyses will include the available cases only unless specified otherwise. Presentation of summary statistics for continuous variables will include N, mean, median, standard deviation, minimum, and maximum values. For categorical variables, the number and percentage under each category will be presented

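### Table 23.2-1 ties follow-up of incomplete procedures to safety; with available-case analysis and no failure rule, these subjects may drop out of the primary stone-free and IPSS results

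*Combined protocol and SAP*

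**What the plan says.** **Glossary.** The Intent-To-Treat row of Table 23.2-1 describes an eligible, consented subject "for whom the Lithotripsy/HoLEP procedure is initiated but not completed (first incision"), and adds: "These patients are followed in accordance with the study follow up schedule for safety and count toward enrollment". No other place in the document says how an incomplete procedure is followed.

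**Analysis sets (Section 11.2.1).** Intent-to-treat (ITT) is every consented subject who "have the Lithotripsy or BPH procedure attempted". As Treated "includes all the ITT subjects who had the Lithotripsy or BPH procedure completed". Per Protocol is a subset of As Treated. Then: "The primary analysis of all the endpoints will be performed for the ITT population".

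**Missing outcomes (Section 11.3).** "The analyses will include the available cases only unless specified otherwise".

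**Primary efficacy methods (Section 11.1.2.2).** For lithotripsy, the proportion with stone clearance at 1 month. For BPH: "The change of IPSS total score at 3-month and 6-month post BPH procedure from baseline will be summarized using descriptive statistics". Neither part says how a subject with an incomplete procedure is counted.

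**Follow-up.** Table 10.1-1 (footnote 4) and Section 10.8.1 require at least one imaging report within 60 days of discharge. Table 10.1-2 and Section 10.8.2 require IPSS at follow-up visits (in the table, unless a catheter is in place) and Qmax if available. Section 10.10 is general: "Each subject in the BPH cohort will be followed up to 6 months (180 days + 60 days) post discharge from HoLEP procedure per site's SOC". None of these makes an exception for an incomplete procedure.

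**Exit rule.** Under Sections 10.6 and 10.10, a lithotripsy subject whose additional procedure does not use the study fiber leaves the study at that procedure.

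**The concern.** Two instructions in one protocol can lead to different data. The glossary row is the specific one for incomplete procedures, and its stated purpose for follow-up is safety. A site could take it as governing and skip imaging, IPSS, QoL and Qmax for these subjects. The analysis plan, however, needs those outcomes, because every attempted procedure is in the primary efficacy population.

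A procedure that could not be finished is plausibly among the least favourable outcomes in a device registry. If such subjects fill places in the cohort of about 100 but have no efficacy outcome, the figures labelled ITT move toward the completed-procedure result, in the device's favour. A conflict between set definitions can be repaired when the data are analysed. A 3-month IPSS that was never taken cannot.

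**Working it through.** **1. The plan's own figure.** Sections 2 and 11.1.1.2 ask for 90 evaluable subjects per cohort and, with 10% attrition, 100 treated: 90 / (1 - 0.10) = 100. Exact (Clopper-Pearson) intervals at n = 90, with the expected count allowed to be non-integer:
- 3% SADE: 90 x 0.03 = 2.7 events, 0.55% to 8.95%, width 8.40% (stated 8.4%).
- 5% SADE: 90 x 0.05 = 4.5 events, 1.52% to 11.75%, width 10.23% (stated 10.2%).

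Both reproduce. They concern the safety endpoint and do not decide this point; they only fix the cohort size of about 100.

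**2. The path of a subject with an incomplete procedure.**
- Enrolled and in the Section 11.2.1 ITT set: yes, because the procedure was attempted.
- Efficacy assessments under Section 10.8 and Tables 10.1-1/10.1-2: due, as for anyone else.
- Efficacy assessments under Table 23.2-1: on the same schedule, but with safety as the stated purpose, so a site may or may not collect them.
- If no imaging or IPSS is obtained: Section 11.3 keeps available cases only, Section 11.1.2.2 has no rule to count the subject as a failure, and the subject leaves the primary result.
- Sensitivity analysis: Per Protocol sits inside As Treated, which Section 11.2.1 limits to completed procedures, so it cannot show the loss.

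**3. A second route for lithotripsy.** The SFR definition (Section 11.1.2) requires no auxiliary procedure between the final study-fiber procedure and 1 month. A subject who has another lithotripsy without the study fiber in that interval would fail the definition, but is exited at that procedure and may have no recorded SFR outcome. Under available-case analysis that subject can also disappear.

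**4. Endpoints not touched.** Successful completion (Section 11.3.1.2), fiber compatibility (11.3.1.3) and hemostasis (11.3.1.6) are assessed at the procedure. The completion endpoint counts an unfinished procedure against the device.

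**5. Size, as an illustration.** The documents give no non-completion rate, expected SFR or expected IPSS change, so all inputs here are assumed. Let c be the incomplete fraction, s the SFR among completers and r the true SFR among incomplete cases. If no incomplete case has imaging:
- reported SFR = s
- SFR over all attempted = (1 - c)s + cr
- overstatement = c(s - r), which is c x s when r = 0.

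Overstatement in percentage points with r = 0:

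| c | s = 70% | s = 80% | s = 90% |
|---|---|---|---|
| 1% | 0.7 | 0.8 | 0.9 |
| 2% | 1.4 | 1.6 | 1.8 |
| 5% | 3.5 | 4.0 | 4.5 |
| 10% | 7.0 | 8.0 | 9.0 |

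For IPSS, let d be the difference in mean improvement between completed and incomplete cases. The overstatement is c x d. With d = 10 to 15 points (incomplete cases not improving at all) it is 0.02 x 10 to 0.02 x 15 = 0.2 to 0.3 points at 2%, 0.5 to 0.75 at 5%, and 1.0 to 1.5 at 10%.

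These are upper values for each c. If every incomplete case is assessed, the overstatement from this source is zero.

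**The case against.** The strongest reply is that the glossary row does not say safety only and waives no assessment. It points to the study's follow-up schedule, and that schedule contains imaging for lithotripsy and IPSS for BPH. Table 23.2-1 also defines a deviation to include departures from required procedures, so a site that skipped required imaging could be in deviation. This stands. A reader might infer that abandoned procedures are excluded from efficacy follow-up by design, or that the ITT efficacy results describe completed procedures only. The documents do not support either inference. They support an ambiguity that may lead there.

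Three further replies also stand in part:
- Qmax is collected only if available for every BPH subject, so a missing Qmax cannot be put down to this row alone.
- Zero improvement after an unfinished HoLEP is a worst case. Section 4.1 describes IPSS and Qmax gains from HoLEP as comparable to those from TURP, so a subject converted to TURP might improve as much.
- The registry is descriptive with no hypothesis (Section 11.1.2.1), so no test result is at risk.

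It could also be said that replacing the glossary row with the Section 11.2.1 definition settles the matter, because the safety wording goes with it. That would settle collection. It would not say how an incomplete procedure without an outcome is counted, nor deal with subjects exited for a lithotripsy without the study fiber.

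**Conclusion.** The point holds as an ambiguity in data collection joined to a gap in the analysis rules. Table 23.2-1 can be read as omitting efficacy assessments after an incomplete procedure, against Section 10.8, Tables 10.1-1/10.1-2 and Section 11.2.1. With available cases only and no failure rule, such subjects may drop out of the SFR, IPSS, IPSS QoL and Qmax results, and the planned Per Protocol analysis would not reveal it. The direction favours the device if incomplete procedures do worse, which is plausible but not shown in the documents.

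The size cannot be derived from the plan. The 3.5 to 4.5 point figure for SFR rests on an assumed 5% of incomplete procedures, an assumed SFR of 70-90% among completers, and all incomplete cases being both unimaged and not stone-free. The correction should be made because it is cheap and because outcomes not collected cannot be recovered later.

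**What to change.** 1. **Table 23.2-1.** Replace the Intent-To-Treat row with the Section 11.2.1 definition, and align the As Treated row, which now says attempted where Section 11.2.1 says completed. State that subjects with an incomplete procedure follow the full schedule in Tables 10.1-1 and 10.1-2, including imaging, IPSS and, if available, Qmax.
2. **Section 11.1.2.2.** Add that, in the ITT analysis, a subject with an incomplete lithotripsy is classified from observed imaging and the SFR definition where available. The subject is counted as not stone-free if there is no imaging, or on exit for an additional lithotripsy without the study fiber before the 1-month assessment. Subjects with an incomplete HoLEP contribute their observed IPSS, QoL and Qmax.
3. **Reporting.** Beside each efficacy result, give the number of incomplete procedures and the number with missing outcomes. The completed-only figure can still be shown on the Section 11.2.1 As Treated set.

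**Cost.** Two glossary rows and a few sentences in the statistical section. No visits are added, since these subjects are already on the follow-up schedule. The SFR and IPSS change may be slightly less favourable. Counting an unimaged incomplete lithotripsy as not stone-free is conservative and would understate the SFR if some of those subjects were in fact clear; the reported counts let a reader judge how much.
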